Repetitive Transcranial Magnetic Stimulation as a Treatment Option for Smoking Cessation

NCT05271175

Date: March 28, 2019

Objectives

This study aims to investigate whether repetitive transcranial magnetic (rTMS) stimulation over the left dorsolateral prefrontal cortex (DLPFC) decreases craving and increases quitting success from smoking in tobacco smokers who wish to quit. This project will also examine whether presentation of provocative visual cues during brain stimulation may produce improved results in reducing craving of smoking as compared to brain stimulation alone.

Introduction

The World Health Organisation (WHO) suggests that smoking is responsible for approximately six million deaths each year¹. Smokers are at greater risk for heart and blood vessel diseases^{2,3}. In addition, smoking causes strokes and coronary heart disease which are the leading causes of death in the United States^{2,3}. Additionally, individuals smoking less than 5 cigarettes per day could be affected by early signs of cardiovascular diseases^{2,3}. Lung diseases caused by smoking include emphysema and chronic bronchitis^{2,3}. Further, smoking causes different types of cancer such as lung, bladder, oesophagus, liver, pancreas and stomach cancer^{2,3}. Individuals who quit smoking sharply, cut their cardiovascular risk after one year and decrease the risk of a heart attack³. Within 2-5 years of quitting, the risk of stroke may reduce to about the same for non-smokers³. Smoking cessation decreases the risk for cancers of the mouth, throat, oesophagus, and bladder drop by half within 5 years³. Ten years after smoking cessation, the risk for lung cancer drops by half³. Due to these and other health risks which were shown to be directly linked to smoking, a global target was announced aiming to reduce the current prevalence of tobacco use in individuals aged 15 and above, by 30%. In Cyprus, the estimated rate of smoking reached 31% in 2005, making it one of the countries with the highest rates in tobacco consumption. While many smokers desire to quit smoking, only 4-7% of them succeed in quitting smoking without supportive treatment⁵.

Several studies have proposed different therapies for quitting smoking. Such therapies include counselling therapies^{6,7,8} and pharmaceutical treatments with the use of products such as the nicotine replacement therapy bupropion (Zyban) and varenicline (Chantix)^{9,10,11,12,13,14}. However, the majority of those attempting to quit smoking are most likely to relapse, as success of such methods is deemed modest. Due to the failure of the current licensed therapies offered for smoking cessation to sustain the initial effect and the fact that patients present high chances of relapse, there is a need to identify new therapeutic approaches. It is essential that such approaches should be related to physiological brain processes, with the aim of understanding, and therefore implementing therapies that are successful beyond immediate behavioural change. Such therapies should ideally directly target brain networks associated with nicotine craving and addiction such as cognitive control and reward processing brain regions.

Tobacco addiction has been linked with the mesolimbic dopaminergic system since the early 90s' in studies that tried to elucidate the role of tobacco addiction *in vitro*³¹. Later studies indicated that brain stress systems play a critical role in tobacco addiction. Smoking as well as smoking cessation affect the regulation of the HPA axis. On one hand, smoking leads to increased release of cortisol and adrenocorticotropic hormone, (a hormone which is produced in the frontal, anterior and pituitary gland of the brain), as well as upregulation and desensitization of nicotinic acetylcholine receptors (nAChRs). It is suggested that the excessive number of responsive nAChRs may contribute to cigarettes' craving and relapse³¹. However, it is important to note that the effects of nicotine in the brain at the molecular level differ from the effects that amphetamines and cocaine

addictions have, and it is vital to understand such differences which may contribute in their better understanding and in potential therapies. At the cellular and system level, tobacco addiction is highly associated with excessive dopamine projections and overflow specifically in structures of the nucleus accumbens, namely the core and the median shell³².

Over the last ten years, neuroscience has advanced in a level that has allowed researchers to implement methods for diagnosis and treatment of various disorders on brain system level. Repetitive Transcranial Magnetic Stimulation (rTMS) is a non-invasive safe treatment option for a variety of neuropsychiatric disorders which has received FDA approval for Depression¹⁵ and Obsessive Compulsive Disorder¹⁶. Neuromodulation interventions with the use of TMS also appear as a promising approach in treating addictions²⁹. The effect of TMS would ideally be to affect brain circuits by inducing neuroadaptations in the cortico-mesolimbic dopamine system, and in the glutamatergic corticolimbic circuitry where dopamine projections are entrenched^{19,20,21}. A review on nine studies focussing on addictions (tobacco, alcohol, cocaine and methamphetamine) investigated outcomes of TMS treatment. Most of the studies applied high frequency (5-20 Hz) rTMS over the left DLPFC. While the underlying mechanism was poorly understood, it was suggested that it may involve dopamine and glutamate function in the cortico-mesolimbic brain circuits and modulation of neuronal activity that mediate cognitive process related to addiction. In this review, support of craving was suggested for nicotine, and in some participants, significant reduced cigarettes consumption was observed. However, changes in craving were not always consistent with decreased smoking³⁰.

A study by Amiaz and colleagues in 2009, suggested that applying TMS on the left DLPFC at high frequency, could offer an innovative treatment option for tobacco dependency²². The intervention included ten daily sessions over the left DLPFC, 20 trains per day at 100% of motor threshold. Each train consisted of 50 pulses at 10 hz with an inter-train interval of 15 seconds. Amiaz investigated the presentation of smoking cues on cigarette consumption, dependence and cravings. A series of 14 pictures were presented to the subjects immediately before the administration of the TMS. Cigarette consumption was measured subjectively through self-report. Craving levels were assessed with the visual analogue scale prior and following the presentation of the visual cues every day. Active TMS was found to significantly reduce both cigarette consumption and nicotine dependence compared to sham stimulation. Additionally, it has been suggested that if rTMS is delivered to the left dorsolateral prefrontal cortex, it could affect decision making which corresponds to addiction and craving¹⁸. On high frequency at 10 hz (24 trains, 5s per train, 25s inner train-interval 1200 pulses with 11.6 minutes, 90% MT) rTMS stimulation of the DLPFC, Jürgen Pripfl³³ and colleagues demonstrated in 14 healthy smokers on cue-induced nicotine craving and resting-state EEG that the rTMS stimulation had an effect on reducing nicotine craving in short term abstinent smokers, with changes in delta activity. This study has supported the idea that stimulation induce effects are mediated by the dopaminergic brain reward system making it a potentially promising treatment for smoking cessation. The DLPFC of addicted individuals has been associated with the experience of craving^{23,24,25}, induced by substance-related cues for nicotine^{26,27,28}. For instance Brody and colleagues (2002) found activation in the DLPFC in “heavy smokers” when exposed to cigarette-related cues compared with non-smokers. Xingbao Li³⁵ has suggested that even one session of high-frequency rTMS (10 Hz) on the left DLPFC can significantly reduce subjective craving induced by smoking cues in nicotine-dependent participants. Further, an fMRI study has suggested that expectancy of smoking following the brain

scan, induced activation in areas that usually correspond to arousal, attention and cognitive control while in participants where smoking was not allowed after the brain scan, such activation was non-existent in response to smoking cues²⁶. It is therefore important that craving induced cues are present; however most studies use such cues prior to the task or treatment. Further, there is no systematic study comparing a condition of rTMS without an external craving cue, versus a condition of rTMS in combination with a smoking craving cue at the time of treatment. So, it would be interesting to investigate whether craving induced cues during rTMS treatment could produce similar results to studies that used a smoking craving cue prior to treatment, comparing it with rTMS at rest, without a smoking craving cue, where treatment will not be dependent to the smoking cue. Finally, across studies on smoking cessation, it has been reported that researchers have used breath carbon monoxide (CO) cut-off values ranging from 4 to 10 ppm to define abstinence in cigarette-smoking cessation. It has been furtherly demonstrated by Murray Jarvik³⁴ that there is a negative correlation between blood nicotine levels and craving for cigarettes while carbon monoxide has shown to correlate significantly with nicotine blood levels.

On the bases of previous research findings, in this study, we are going to compare tobacco cravings between three groups (two experimental and one control) of tobacco smokers that wish to quit smoking, after a five-day treatment of five 3-minute theta burst repetitive transcranial magnetic stimulation which will be applied over the left DLPFC. We hypothesize that:

- (A) The two experimental groups (group A that will receive real rTMS, four sessions per day of intermittent theta burst, for three minutes per session, for five consecutive days, while watching a smoking video as a cue for craving, and group B group that will receive real rTMS, four sessions per day of intermittent theta burst, for three minutes per session, for five consecutive days, with no presentation of the smoking video as a cue for craving, but presentation of a neutral video) will present lower craving scores in relation to their baseline measures,
- (B) The two experimental groups, (groups A and B) will present lower craving scores in relation to the placebo group (group C will receive sham rTMS four sessions per day of intermittent theta burst, for three minutes per session, for five consecutive days, while watching a smoking video as a cue for craving) after the end of rTMS treatment,
- (C) We investigate the difference between the presentation or absence of visual cue among the two experimental groups (group A and B that will both receive real rTMS, with the difference that group B will not be presented a smoking video as cue for craving) as to whether presentation or absence of stimuli influences outcome of craving scores.

Method

Participants

Recruitment of participants will be done through public advertisements of the study, as participants belong in the healthy population. Individuals who agree to participate in this study will be volunteers. The minimum number of participants required was determined by an a priori power analysis where at least a sample size of 100 participants was suggested. (*Measures that suggested this sample size were determined by the mixed model, a small to medium effect size (0.4), at an alpha level of probability of 0.05).

Inclusion criteria of participants will be: (a) to be native speakers of the Greek language, (b) to be over the age of 18, (c) to be tobacco dependent users that wish to quit smoking.

Exclusion criteria of participants will be: (a) individuals with metallic parts inside or near the skull, (b) dependency of any other substances apart from nicotine and caffeine.

For the purposes of this study, participants will be formed into three groups. The groups will be as described below:

(A) An experimental group of 34 participants that satisfy all criteria for inclusion. This group will receive real rTMS, four sessions per day of intermittent theta burst, for three minutes per session, for five consecutive days, while watching a smoking video as a cue for craving;

(B) An experimental group of 34 participants that satisfy all criteria for inclusion. This group will receive real rTMS, four sessions per day of intermittent theta burst, for three minutes per session, for five consecutive days, with no presentation of the smoking video as a cue for craving, but a neutral video;

(C) A control group of 34 participants that satisfy all criteria for inclusion. This group will receive sham rTMS four sessions per day of intermittent theta burst, for three minutes per session, for five consecutive days, while watching a smoking video as a cue for craving.

Design

This is a randomized, double-blind, sham-controlled study.

Procedure

Prior to the study

After advertisement of the study, potential participants will be able to contact the researcher via contact details that will be given on the advertisement. The researcher will then perform a screening interview (either by phone or email correspondence) regarding the eligibility of participants. The questions will include demographics and contact details: a) telephone number, b) email address, c) sex, d) education and occupation, e) age; and the screening will involve questions regarding eligibility: f) “how many cigarettes do you smoke per day?”, g) “for how long have you been a smoker?”, h) “has there been any period in your life that you managed to quit smoking; if yes for how long and how did you manage to do it?”, i) “are you dependant on any other substances e.g. alcohol/drugs/benzodiazepines apart from caffeine and nicotine”. These questions will be asked in Greek. If individuals meet the criteria and wish to continue, the researcher will arrange with participants details regarding their visit to the site.

At the research site

Participants will arrive at the Cyprus rTMS Centre, will receive all the required information about their participation, and if agreed, they will sign the consent form and will be led to the testing room. Participants will then complete three questionnaires on a PC, prior to the beginning of the experiment. The questionnaires are all described in Materials section and they are attached in the Appendix. All participants will undergo a breath carbon monoxide (CO) measure prior to each TMS session of each day with the use of a smokerlyzer. Further information about its use is described in the section below.

The researcher will then take the appropriate head measures using the 10-20 system and then will place a cap on the participant's head. The participant will sit on the TMS chair and the researcher will place the (real/sham) TMS coil on the participant's left DLPFC and start the session. While participants will be receiving TMS, they will be presented with a smoking video as a cue for craving, throughout each TMS session (except for one group that they will not be presented with a cue craving video, but with a neutral video). There are two available videos, and those will be presented in a randomised manner for each participant. After each session, participants will have a forty-five minute break and then return for the next TMS session. Once done with all five days of TMS therapy, they will be again assessed with the three questionnaires.

To protect personal data and for conditions to be double-blind (participants will not know whether they receive real or sham TMS and researcher will not know whether they administer real or sham TMS), participants will be pseudo-anonymised on an excel database and will be assigned in a randomised manner to each defined group. Demographic and personal data of participants will be confidential only to the researchers involved in the study and will be protected and handled according to the Data Protection Act 2018 and the ICH Good Clinical Practice for data protection. Recorded data of participants will include: demographic details, data of self-report questionnaires at baseline and follow up measures, and CO breath levels.

Following TMS treatment

Following the end of the rTMS treatment, participants will be contacted again to complete the three questionnaires. This will be done at one week, one month and six months post-TMS treatment.

Materials

Questionnaires

The tools used in this study are three questionnaires:

- The Fagerstrom Test of Nicotine Dependence (in Greek),
- The Factor Structure of Tobacco Craving-Short Form (will be adjusted to Greek),
- The Perceived Stress Scale (in Greek).

These questionnaires will be administered to each participant prior to the first day of TMS treatment, after the last day of TMS treatment, after one week, after one month, and after six months. Participants will complete the questionnaires on a 14" laptop at baseline and first follow up, and then online during the remaining follow ups. The aim of the questionnaires will be to test for nicotine dependence, levels of craving, and screening for anxiety levels of participants at different time points. Those data will then be used for within and between participants' analyses. Further, participants will be asked through a visual analogue scale ranked from 1-100 "How much do you want to smoke right now?", prior and after each TMS session, as previously used by Revital Amiaz in similar methodology studies, to assess cue-induced craving of participants.

Smokerlyzer

Smokerlyzer is a non-invasive tool that measures the amount of CO on a smoker's breath and establishes smoking status biochemically. It will be used prior to each TMS session every day for each participant and its measures will be later used for analyses purposes.

Craving Videos

Two videos will be used during the TMS sessions, presented in a randomized manner. The first video is a smoking video which lasts for three minutes and its purpose is to be a cue for inducing craving. The other video used will be a neutral video, illustrating daily tasks that do not involve smoking. This video will be used as a control video.

TMS Protocol

This study will attempt to use accelerated theta burst stimulation of TMS, and specifically the 3-minute FDA-approved protocol for depression. rTMS will be applied to each participant for a period of five consecutive days. Each day will consist of four sessions of the 3-minute theta-burst stimulation with a 45-minute gap (which is the optimal gap) between sessions. The protocol includes 2 seconds of stimulation on the left dorsolateral prefrontal cortex which is followed by an 8 second pause. There will be 600 pulses in total for each 3-minute session. The site of stimulation will be the left DLPFC. It will be measured by using the 10-20 system, it will be determined by the Beam F3 software and it will be at 100% of the motor threshold.

Planned Analysis

The data will be analysed in SPSS. Analyses of hypotheses will be carried out with a mixed model (repeated measures within and between factors). Within factors will be determined from the craving scores in the baseline and follow ups from the three questionnaires, and CO measures. Between factors will be determined by the three experimental groups. Analyses will be adjusted for sex, age and visual stimuli.

Expected outcomes & Benefits of the study

Few studies have examined smoking cessation through a TMS treatment. Further, there is a question as to whether exposure to behavioural cues before or during TMS treatment may influence craving outcomes, which may improve our understanding in the mechanisms that influence successful outcome, while using induced plasticity methods. While we expect that experimental groups will have significantly decreased craving scores compared to control group, generally this study will aid in our understanding regarding potential options for smoking cessation and possibly for other addictions with similar physiological mechanisms.

References

1. World Health Organization. (2015). WHO global report on trends in tobacco smoking 2000-2025. Geneva: WHO.
2. US Department of Health and Human Services. (2014). The health consequences of smoking—50 years of progress: a report of the Surgeon General. Atlanta, GA: US Department of Health and Human Services, Centers for Disease Control and Prevention, National Center for Chronic Disease Prevention and Health Promotion, Office on Smoking and Health, 17.
3. US Department of Health and Human Services. (2010). How tobacco smoke causes disease: What it means to you. Atlanta: US Department of Health and Human Services, Centers for Disease Control and Prevention. National Center for Chronic Disease Prevention and Health Promotion, Office on Smoking and Health.
4. European Commission (2015). Retrieved from: <https://goo.gl/1qkJFx>
5. Brody, A. L., & Cook, I. A. (2011). Manipulation of cigarette craving with transcranial magnetic stimulation. *Biological psychiatry*, 70(8), 702.
6. Goldstein, M. G., Niaura, R., Willey, C., Kazura, A., Rakowski, W., DePue, J., & Park, E. (2003). An academic detailing intervention to disseminate physician-delivered smoking cessation counseling: smoking cessation outcomes of the Physicians Counseling Smokers Project. *Preventive medicine*, 36(2), 185-196.

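### Quitting success is a stated aim, but no post-treatment assessment is described as recording smoking status and no abstinence outcome is planned

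*Combined protocol and SAP*

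**What the plan says.** The Objectives set two treatment aims, namely that rTMS "decreases craving and increases quitting success from smoking in tobacco smokers who wish to quit", plus the comparison with and without a smoking cue. The title presents rTMS as a smoking cessation treatment.

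What is to be collected:

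- **Carbon monoxide** (At the research site): "All participants will undergo a breath carbon monoxide (CO) measure prior to each TMS session of each day with the use of a smokerlyzer". The Smokerlyzer section gives the same timing.
- **Follow-up** (Following TMS treatment): "Following the end of the rTMS treatment, participants will be contacted again to complete the three questionnaires", at one week, one month and six months. The same three are also given after the last treatment day. The Questionnaires section puts the later three rounds online.
- **Purpose of the questionnaires** (Questionnaires): "to test for nicotine dependence, levels of craving, and screening for anxiety levels of participants at different time points".
- **Cigarettes per day** (Prior to the study): described only as a screening-interview question.
- **Data recorded** (At the research site): "Recorded data of participants will include: demographic details, data of self-report questionnaires at baseline and follow up measures, and CO breath levels".

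What is to be analysed (Planned Analysis): a repeated-measures mixed model, in which "Within factors will be determined from the craving scores in the baseline and follow ups from the three questionnaires, and CO measures".

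The Introduction mentions abstinence thresholds only as other studies' practice: "researchers have used breath carbon monoxide (CO) cut-off values ranging from 4 to 10 ppm to define abstinence in cigarette-smoking cessation". It also reports, from a review of TMS in addiction, that "changes in craving were not always consistent with decreased smoking".

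**The concern.** An aim needs an outcome that can answer it. Here the second half of the treatment objective has no measurement described after treatment, no definition of success, no time point and no analysis. Craving cannot stand in for it, because the plan's own literature summary says the two can diverge.

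A sponsor who follows this plan exactly reaches six months with craving, dependence and stress scores but no defined quit rate. Any statement about cessation would then be inferred from craving or constructed after the data are seen. The loss is also hard to undo: smoking status not asked at 1 week, 1 month and 6 months cannot be reliably reconstructed later.

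**Working it through.** **Step 1. Follow the aim through the plan.**

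| Element | Where | Craving | Smoking status or quitting |
|---|---|---|---|
| Objective | Objectives | yes | yes |
| Hypotheses A, B, C | end of Introduction | yes, all three | no |
| Visual analogue scale, around each session | Questionnaires | yes | no |
| CO | At the research site; Smokerlyzer | – | treatment week only, no threshold adopted |
| End of treatment, 1 week, 1 month, 6 months | At the research site; Following TMS treatment; Questionnaires | yes | not described |
| Analysis | Planned Analysis | yes | CO as a measure; no abstinence outcome |

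**Step 2. Count the measurements.** Four sessions a day for five days (TMS Protocol) give 4 x 5 = 20 CO readings. Each precedes a session, so even the last is taken before treatment ends. CO readings scheduled at 1 week, 1 month or 6 months: 0. Post-treatment assessments described as recording smoking status: 0 of 4.

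**Step 3. Could the treatment-week CO supply the outcome?** It bears on smoking during those five days. It says nothing about the following six months, and no cut-off in the cited 4 to 10 ppm range is adopted to turn a reading into a status.

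**Step 4. How precise would an added quit outcome be?** The plan has no figure of its own to reproduce here. The stated minimum of 100 rests on an effect size of 0.4 and is not tied to abstinence. The inputs are 34 per group (Participants) and sham quit rates of 5.5% and 7%, taken from the 4–7% unaided range in the Introduction, which has no time window. All active-group rates and counts below are assumptions.

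*Interval for a difference (Newcombe).* With Wilson limits (l, u) for each proportion p and d = p1 − p2:

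lower = d − √[(p1 − l1)² + (u2 − p2)²]; upper = d + √[(u1 − p1)² + (p2 − l2)²]

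- Sham 2/34: p2 = 0.059, Wilson 0.016 to 0.191.
- One active group 8/34: p1 = 0.235, Wilson 0.124 to 0.400. d = 0.176; lower = 0.176 − √(0.111² + 0.132²) = 0.004; upper = 0.176 + √(0.165² + 0.043²) = 0.347. That is 17.6 points (0.4 to 34.7).
- Pooled active 16/68: p1 = 0.235, Wilson 0.150 to 0.349. The same formula gives 17.6 points (1.9 to 29.7).

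*Power (two-sided Fisher exact test, alpha 0.05).* This sums the binomial probabilities of all tables with p ≤ 0.05.

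| Sham v active (assumed) | 34 v 34 | 34 v 68 |
|---|---|---|
| 5.5% v 20% | 28% | 45% |
| 7% v 25% | 41% | 60% |
| 7% v 30% | 60% | 80% |

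A quit outcome can therefore be estimated in this trial, but only loosely. That supports making it secondary and reporting intervals.

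**Step 5. Look-back at end of treatment.** A 7-day window asked straight after a five-day course reaches back 7 − 5 = 2 days or more before day 1. It would mix pre-treatment smoking into the outcome.

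**The case against.** **The questionnaires may already ask about smoking.** They are in an Appendix that was not available, and the nicotine dependence test is repeated at all four post-treatment assessments. It may contain a consumption item. This limits the count of 0 of 4 to what the plan describes. It does not supply a quit outcome, because the plan derives no smoking status from any questionnaire.

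**CO may cover it.** The Smokerlyzer section says the device establishes smoking status, and Planned Analysis can be read loosely as placing CO at follow-up. The two sections that schedule CO tie it to TMS sessions, and the later follow-ups are online, so the narrower reading is the better one. The ambiguity is still the sponsor's to settle.

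**Craving is the real outcome.** All three hypotheses and the expected group difference concern craving, and deleting a phrase would cure the mismatch. This is the strongest point: the planned craving comparisons are unaffected. But the aim and the title now promise more than the data described can deliver.

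**The numerical example is fragile.** Its counts are assumed. For 8/34 v 2/34 the Newcombe interval just excludes zero while Fisher's test gives p = 0.083. That is fair. The example shows imprecision only, and the conclusion does not rest on it.

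**Conclusion.** The concern holds and should be fixed. A named aim has no described post-treatment measurement (0 of 4 assessments), no CO after the treatment week (0 of 20 readings) and no definition or analysis of abstinence. The absence of an abstinence outcome and analysis is plain from the text. The measurement count assumes that the unseen questionnaire items add no smoking-status question beyond the stated purposes, and that CO is taken only when the scheduling sections say. If a consumption item exists, the plan would still need to say how quitting is derived from it. The precision and power figures are illustrations under assumed rates and full response.

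**What to change.** **Either measure quitting:**

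1. At 1 week, 1 month and 6 months, add two items: any smoking in the past 7 days, and current cigarettes per day. At end of treatment, add cigarettes per day only.
2. In Planned Analysis, prespecify self-reported 7-day abstinence at 6 months as a secondary outcome. Count non-responders as smoking, and report the number responding in each group so that uneven response is visible.
3. Report abstinence by group, with risk differences and 95% CIs for A v C, B v C and pooled A+B v C. Label the results as imprecise and not biochemically verified.
4. State in Planned Analysis that the CO measures cover the treatment week only, as the scheduling sections indicate. If follow-up CO was intended, the schedule must say so.

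**Or narrow the claim:** remove quitting success from the objective and restrict conclusions to craving.

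**Cost.** Two extra questions on questionnaires already being sent, with no new visit or device. The estimate will be self-reported and of low precision. Group B watches a neutral video while A and C watch the smoking video, so B v C and the pooled contrast mix video content with stimulation. A v C is the contrast with the same video and should be read first.

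### Hypothesis (B) compares A and B with sham group C, but B differs from C in video as well as stimulation; only A versus C isolates rTMS, and the plan neither names that contrast nor codes the video term

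*Combined protocol and SAP*

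**What the plan says.** **Groups (Participants).** There are 34 participants in each group. A gets real stimulation with the smoking video, B real stimulation with the neutral video, and C sham stimulation with the smoking video.

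**Hypotheses (Introduction).** Hypothesis (B) reads "The two experimental groups, (groups A and B) will present lower craving scores in relation to the placebo group", assessed once treatment has ended. Hypothesis (C) compares A with B to study the cue.

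**Model (Planned Analysis).** The plan is a mixed model in which "Between factors will be determined by the three experimental groups". It then adds: "Analyses will be adjusted for sex, age and visual stimuli". It names no contrast, does not say whether A and B are pooled or tested separately against C, and does not define the visual stimuli variable.

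**Videos.** The Craving Videos section says: "The first video is a smoking video which lasts for three minutes and its purpose is to be a cue for inducing craving". The section on procedures at the research site shows the smoking video to everyone "except for one group that they will not be presented with a cue craving video, but with a neutral video", which fixes video by group. The same paragraph also says: "There are two available videos, and those will be presented in a randomised manner for each participant". The Craving Videos section likewise speaks of randomised presentation.

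**The concern.** Hypothesis (B) is where the trial claims that rTMS beats sham. One of its two comparisons, B with C, changes two things at once: the stimulation, and a video meant to provoke the outcome being measured. If the smoking video raises craving, B can look better than C although rTMS does nothing. If viewing the cue during treatment lowers later craving, B can look no better than C although rTMS works.

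The adjustment for visual stimuli might be meant to deal with this. Whether it does depends on coding that the plan does not give. Two analysts following the same text could test different effects and reach different conclusions about rTMS.

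**Working it through.** **Inputs.** From Participants: 34 per group and alpha 0.05. Assumed: two-sided tests, claims counted in the predicted direction, one score per person in SD units without baseline adjustment, and a video effect *g* (smoking minus neutral) of stated size. The documents give no value for *g*.

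**The plan's own figure.** No power is given for any contrast. The only related figure is the minimum of 100, allocated as 3 × 34 = 102. The text states an effect size of 0.4 but neither its metric nor the power. Reading 0.4 as Cohen's f in a three-group one-way ANOVA with an assumed 95% power gives 102. That would be an omnibus basis and does not show which contrast was meant.

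**Step 1: what each contrast estimates.** Let τ be the rTMS effect, and assume that effects add. Relative to sham with neutral video, the means are A = τ + g, B = τ, C = g. Then:

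- A − C = τ
- B − C = τ − g
- (A + B)/2 − C = τ − g/2

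Without additivity, A − C is still the rTMS effect in the presence of the smoking cue, and B − C = (A − C) − (A − B) still subtracts the cue difference. With no sham-plus-neutral group, a stimulation-by-video term cannot be estimated (4 columns, rank 3), so additivity cannot be tested.

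**Step 2: what the video term does.**

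- *Three-level group plus video:* intercept, two group indicators and video make 4 columns of rank 3. Group and video effects cannot both be estimated. Intercept plus video alone has rank 2, so the group test adjusted for video has 3 − 2 = 1 df instead of 2, and that 1 df is A versus C.
- *Real/sham plus video:* 3 columns, rank 3. The rTMS coefficient has weights 1, 0, −1 on the means of A, B, C, which is A − C.
- *Real/sham without video:* weights 0.5, 0.5, −1, which is the pooled contrast carrying g/2.

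**Step 3: illustration with no rTMS effect and a smoking video that raises craving by g.** For a true difference d, the noncentrality is δ = d / √(1/n₁ + 1/n₂), and the claim rate is P(T > t₀.₉₇₅) under noncentral t. For B versus C at g = 0.2: δ = 0.2/√(2/34) = 0.825, 66 df, critical value 1.997, giving 12.6%. For pooled: d = 0.1, δ = 0.1/√(1/68 + 1/34) = 0.476, 99 df, critical value 1.984, giving 6.8%. The both and either rows come from simulation (400,000 trials per setting).

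| False rTMS claim, % | g = 0 | 0.2 | 0.3 | 0.5 |
|---|---|---|---|---|
| A vs C | 2.5 | 2.5 | 2.5 | 2.5 |
| Both required | 0.5 | 1.3 | 1.7 | 2.3 |
| Pooled vs C | 2.5 | 6.8 | 10.5 | 21.7 |
| B vs C alone | 2.5 | 12.6 | 22.9 | 52.9 |
| Either counts | 4.5 | 13.9 | 23.7 | 53.1 |

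**Step 4: the opposite direction.** Suppose rTMS lowers craving by 0.69 SD, the difference that 34 versus 34 detects with 80% power (δ = 0.69/√(2/34) = 2.845), and the smoking video also lowers craving.

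| Power, % | video lowers by 0 | 0.2 | 0.3 | 0.5 |
|---|---|---|---|---|
| A vs C | 80 | 80 | 80 | 80 |
| Both required | 69 | 47 | 33 | 11 |
| Pooled vs C | 90 | 79.4 | 72.1 | 54.6 |
| B vs C alone | 80 | 51 | 35 | 12 |

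**The case against.** **The plainest reading of hypothesis (B) is that both groups must be lower than C.** This stands. If both contrasts must be significant, false claims cannot exceed the 2.5% of A versus C, and the cost is lost power, most of all if the smoking video lowers craving. A reader might take the 13 to 53% as the trial's error rate. The documents do not support that: nothing makes B versus C alone, or either contrast, the rTMS test. Nor does anything state that both are required or that pooling is excluded.

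**The adjustment may already be the remedy.** In part. A real/sham model with video does give A − C. But the plan names a three-level group factor, where video is aliased. It would also be wrong to say that the term does nothing there, since it reduces the group test to 1 df.

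**A video effect on the analysed scores is conjecture.** Its size is. The rating after each session is taken "to assess cue-induced craving of participants", but the Planned Analysis builds its within factors from the three questionnaires and CO and does not list that rating. The questionnaires come after the last treatment day and then at one week, one month and six months, the last three online with no video described. An acute effect could reach the end-of-treatment questionnaire, but persistence is unknown.

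**The Objectives might seem to need a sham control for rTMS without a cue.** They ask "whether presentation of provocative visual cues during brain stimulation may produce improved results in reducing craving of smoking as compared to brain stimulation alone". That is A versus B, which hypothesis (C) covers, so the missing sham-plus-neutral group limits generality and does not leave that question unanswered.

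**The neutral video might seem to unblind the operator to group B.** The documents do not say that the operator sees the screen or knows the pairing, so this is not claimed.

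**If videos were randomised within participants, the aliasing would not be complete.** Correct. Step 2 relies on video being fixed by group, as the group definitions state.

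**Conclusion.** The point holds as a fault of specification and interpretation that should be fixed. The B-versus-C part of hypothesis (B) does not isolate rTMS, and the visual stimuli term either is aliased with group or silently determines the contrast, depending on coding that is not given. A reader might infer that the design cannot test rTMS at all. It can: A versus C is a clean randomised comparison, valid for rTMS delivered with the smoking cue.

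The structural results (bias of g for B versus C and g/2 pooled under additivity; rank 3 of 4 columns) follow from the group definitions. The percentages do not have that standing. They rest on an assumed video effect of 0.2 to 0.5 SD present at the analysed time point, and on readings that the plan leaves open without adopting.

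**What to change.** 1. Keep the three-level group factor and name the contrasts: A versus C as the test of rTMS versus sham, stated to apply with the smoking cue; A versus B as the cue test for hypothesis (C); B versus C reported only as a combined stimulation-and-video comparison. Do not pool A and B for an rTMS claim.
2. Remove visual stimuli as a covariate beside group; keep sex and age. The removal is safe only with three-level coding and named contrasts, because in a real/sham model dropping video yields the pooled, confounded contrast.
3. Reconcile the randomised-presentation wording in the site-procedure and Craving Videos sections with a video fixed by group.

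The cost is wording only; groups and sample size do not change. The downside is that the rTMS claim is confined to the cue condition and rests on 34 versus 34, which detects 0.69 SD at 80% power in a simple two-group test. With baseline as a covariate and an assumed correlation r of 0.3, 0.5 or 0.7, multiplying by √(1 − r²) gives 0.66, 0.60 or 0.49 SD.
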